## Background

In Denmark, around 12,700 patients undergo cesarean delivery (CD) annually, constituting approximately 20% of all childbirths in the country (Danish Birth Registry 2023). Worldwide, the number is increasing yearly with more than 20 million CDs performed annually (Betran et al. 2021).

Postoperative pain after CD is typically moderate to severe in intensity and still constitutes a significant challenge, balancing effective pain relief and potential side effects ([name], [name] and [name] 2023; Lindelof et al. 2022; Roofthooft et al. 2021). Correlations between moderate to severe acute pain and the development of persistent pain after CD is still unclear (Eisenach et al. 2008; Nikolajsen et al. 2004; Sun and Pan 2019; Yimer and Woldie 2019).

Persistent pain is observed after various surgical procedures, posing a challenge for many patients (Kehlet, Jensen, and Woolf 2006). The reported incidence of persistent pain after CD varies considerably among studies; in a review of persistent pain after CD (Sun and Pan 2019) 11-27% of patients reported pain after six months. Four Danish studies have addressed acute pain following CD in the Danish population ([name],

[name], and [name] 2023; Hansen et al. 2019; Lindelof et al. 2022; Nikolajsen et al. 2004). One of these studies has also examined the occurrence of persistent pain (Nikolajsen et al. 2004); in a single-center study including 220 patients with a mean follow-up time of 10.2 months (range 6-17.6). Nikolajsen et al. concluded that 5.9% of the patients experienced pain from the cesarean scar area, daily or almost daily. To our knowledge, no studies have prospectively explored the potential effects of postoperative pain on functional outcomes and the ability to care for the infant beyond the early postoperative period.

Both pre-, intra-, and postoperative factors have been associated with an increased risk of persistent pain after surgery (Kehlet, Jensen, and Woolf 2006; Sun and Pan 2019). Current approaches to persistent pain prevention aim to use surgical techniques that avoid nerve damage, reduce tissue injury, optimize multimodal analgesia, and reduce acute postoperative pain (Kehlet, Jensen, and Woolf 2006; Sun and Pan 2019, Tan et al. 2022). The current predominance of evidence emphasizes an association between the severity of acute pain after surgery and the development of persistent pain (Yimer and Woldie 2019).

Postsurgical persistent pain is a significant, often unrecognized clinical problem that causes distress and diminishes the quality of life for patients (Kehlet, Jensen, and Woolf 2006). Despite advances in understanding the factors contributing to persistent post-surgical pain and an increased focus on identifying patients at risk, the management and prevention of post-surgical persistent pain are still inadequate (Kehlet, Jensen, and Woolf 2006).

It is important to gain further insights into this population, and we have a unique opportunity to do so by following the national cohort from the ongoing Danish multicenter cohort study on pain after cesarean section ([name] et al. 2023) over an extended follow-up period. This involves continued prospective registration of patient-reported outcomes in the months and years after the CD, thereby investigating the occurrence of both acute and persistent pain after CD.

## Objective

This study aims to describe the occurrence of persistent postoperative pain in a cohort of Danish patients who have undergone elective CD. The outcomes are focused on pain levels, the impact of pain on physical function, and neuropathic pain characteristics in the months and years following the CD. The study also aims to explore the relationship between persistent and acute pain.

## Method

### Study design

Prospective Danish multicenter cohort study based on Patient-Reported Outcome Measures (PROM) collected by SMS-based questionnaires and clinical data from electronic health records.

## Inclusion criteria

Patients, aged > 18 years, who undergo planned CD under spinal anesthesia.

Patients who speak and read Danish and can provide informed consent to participate.

Patients who have a smartphone that can receive an SMS with a link to a questionnaire that can be accessed on an online website on the phone. Patients who, after participating in the Danish multicenter cohort study on pain after CD ([name] et al. 2023), consent to continue receiving questionnaires about persistent pain.

## Number of participants

We aim to include at least 300 patients from all 5 regions in Denmark. The final number of participants will depend on the cohort size from the ongoing study ([name] et al. 2023).

## Outcomes

All outcomes related to **pain**, refer to pain in or around the surgical area. Assessments are conducted at 5 weeks, 2, 3, 6, and 12 months, and after that every 6 months until 3 years after surgery.

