#### *Exploratory outcomes*

1. Recall of acute pain at 12 and 24 hours after CD. Asked 12 months after CD.
2. Percentage of patients experiencing pain with an NRS > 3 at 1, 2, 3, and 12 months, as well as 2, 3, 4, and 5 years after CD.
3. Association between severe acute pain (NRS > 6) during the first 24 hours and the occurrence of persistent pain at 6 and 12 months after CD.
4. Prevalence of chronic pain before pregnancy.
5. Prevalence of chronic pain before pregnancy and its association with the development of persistent pain at 6 and 12 months, and 2, 3, 4, 5 years after CD.
6. Association between uterine exteriorization versus in situ repair in CD and the occurrence of persistent pain at 6 and 12 months, as well as 2, 3, 4, and 5 years after CD.

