## Data collection

The questionnaires are sent at fixed time intervals: at 5 weeks, 2 months, 3 months, 6 months, and 12 months, and thereafter every 6 months until 5 years after CD. Reminders are sent the day after the initial questionnaire in case of no response. All questionnaire data are entered directly into the closed and secure system REDCap. Data from journal entries are also entered into REDCap. At all hospitals, a data manager can retrieve data for the patients included in the project. The primary investigator holds the overall responsibility for the data.

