### *Data Processing and statistics*

All data will be handled in the REDCap database. Descriptive statistics will be used to analyze data. Continuous data will be summarized as median (interquartile range) or mean (standard deviation) if the data is normally distributed, and categorical data as frequency (percentage). Subgroup analyses are planned for: Severe acute pain and the association of persistent pain; the association between uterine exteriorization versus in situ repair and the occurrence of persistent pain; as well as the prevalence of chronic pain before pregnancy and its association with the development of persistent pain. We will try to minimize missing data as much as possible by sending questionnaires directly to the participants mobile phones and sending reminders. The amount of missing data will be accounted for when describing data. The sample size is determined by convenience, with an expected participation rate of approximately half of the 700 patients from the initial cohort study agreeing to continue with the questionnaires on persistent pain. We analyze the data when the last of the included patients have completed the 12-month questionnaire and again after every year.

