### *Patient characteristics*

- Pre-pregnancy BMI
- Parity
- Indication for CD: Maternal request/Previous CD as the only indication/Breech presentation/Maternal indication/Obstetric indication/Fetal indication/Other indication.
- Previous number of CD: 0, 1, 2, 3, or  $\geq 4$
- Previous abdominal surgeries: Yes/No. If yes: Laparoscopic or laparotomy
- Chronic pain patient, and/or receiving regular opioid and/or other pain treatment besides NSAIDs and PCM prior to pregnancy: Yes/No
- Inflammatory bowel disease (Crohn's disease or ulcerative colitis): Yes/No
- Pregnancy-related illness? No/Gestational hypertensive disorder (Preeclampsia including HELLP, Gestational hypertension)/Gestational diabetes, Other).

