### *Operation information*

- Operation time (minutes)
- Intraoperative bleeding. ml.

- Has the uterus been exteriorized during the operation? Yes/No/The information was not found in the medical record.
- Postoperative bleeding within the first 48 hours requiring blood transfusion. Yes/No
- Reoperation within the first 30 days: Yes/No. If yes: Abdominal bleeding/Vaginal bleeding/Suspected retained tissue or endometritis/Infection at the incision site/other reason

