## Appendix 1-8

1. Project approval from the research lawyer at The Capital Region (Region Hovedstaden) Center for Data Notifications. Approval number P-2023-90.
2. Ethical approval assessment, journal number F-23004686.
- 3-6. Data agreements for research projects between the regions.
7. Collaboration agreement.
8. Overview of the questions that are set up as questionnaires in REDCap and sent to the patient via a link in SMS.

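### Pain is followed to 5 years after the index cesarean, but nothing listed records a later delivery or abdominal operation, so late estimates can count new surgical pain as persistent pain

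*Protocol*

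**What the plan says.** - **Definition of pain.** Under Outcomes, all pain outcomes "refer to pain in or around the surgical area". Which operation caused the pain is not part of the definition.
- **Length of follow-up.** Data collection sends questionnaires at 5 weeks and 2, 3, 6 and 12 months, and "thereafter every 6 months until 5 years after CD". The Outcomes section stops at 3 years. The two must be reconciled, but this point holds under either.
- **Late estimates.** Exploratory outcome 2 is "Percentage of patients experiencing pain with an NRS > 3 at 1, 2, 3, and 12 months", and then at 2, 3, 4 and 5 years. Outcome 6 is "Association between uterine exteriorization versus in situ repair in CD and the occurrence of persistent pain at 6 and 12 months", again extended to 2-5 years. Outcome 5 (chronic pain before pregnancy) covers the same years. Under Data Processing and statistics, data are analyzed once the last patients "have completed the 12-month questionnaire and again after every year".
- **Events recorded.** Patient characteristics has "Previous number of CD: 0, 1, 2, 3, or" four or more, and earlier abdominal surgery. Both are history before the index cesarean. Operation information has "Reoperation within the first 30 days: Yes/No". The remaining chart variables cover the index anesthesia, early pain treatment, the index stay and ileus within 7 days.
- **Questionnaire.** Development and validation of questions states 23 short questions, which matches the 23 numbered secondary outcomes. None concerns a new pregnancy, delivery or operation. Appendix 8 is described as an "Overview of the questions that are set up as questionnaires in REDCap"; its content was not available.

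**The concern.** A repeat cesarean involves the same area as the index one, so a definition by site cannot tell pain that has persisted from pain that a new operation has caused. The protocol itself shows that repeat cesareans are common enough to plan for: it lists a previous cesarean as a stand-alone indication and counts earlier ones up to four or more. Over 2 to 5 years in women of childbearing age, further deliveries are to be expected, yet none would be visible in the data.

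Three things are at stake:

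- The NRS > 3 prevalence in exploratory outcome 2 is too high whenever pain is more frequent after a new event than true persistence is.
- The uterine-repair association in outcome 6 is probably diluted, because pain from a later operation has nothing to do with how the uterus was repaired at the index cesarean.
- The two secondary items that refer to the infant (items 6 and 12) become ambiguous once there is another child.

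This is a question of what is collected. A statistical analysis plan can restrict or stratify only on events that were recorded with a date.

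**Working it through.** **Sample size.** The protocol expects about half of 700 patients: 0.5 × 700 = 350, in line with the aim of at least 300. There is no power calculation to reproduce.

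**Prevalence, outcome 2.** Let p be the true share with NRS > 3 from the index cesarean, f the share with a new delivery or abdominal operation before the assessment, and q the NRS > 3 rate among those women. Then

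observed = (1 − f)·p + f·q.

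Inputs: p = 5.9%, 11% and 27% are borrowed from Background, where they refer to other pain definitions and times (daily or almost daily scar pain; any pain after six months). f and q are assumptions; the protocol gives neither.

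Example: p = 5.9%, f = 20%, q = 15% gives 0.8 × 5.9 + 0.2 × 15 = 4.72 + 3.00 = 7.72%.

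| f | p = 5.9%, q = 15% to 25% | p = 11%, q = 15% to 25% |
|---|---|---|
| 10% | 6.81% to 7.81% | 11.40% to 12.40% |
| 20% | 7.72% to 9.72% | 11.80% to 13.80% |
| 30% | 8.63% to 11.63% | 12.20% to 15.20% |

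Over f = 20-30% the ratio of observed to true is 7.72/5.9 = 1.31 to 11.63/5.9 = 1.97 for p = 5.9%, and 11.8/11 = 1.07 to 15.2/11 = 1.38 for p = 11%. With p = 27%, q lies below p and the observed value falls to 23.4-26.9% (f = 5-30%), so there is no inflation.

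**A second model.** If index pain is kept and new pain is added, observed = p + f·(1 − p)·q. With q = 11-27% and f = 5-30%, the added amount runs from 0.11 × 0.05 × 0.89 = 0.5 points (p = 11%) to 0.27 × 0.30 × 0.941 = 7.6 points (p = 5.9%).

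**Against sampling error.** The 95% half-width at N = 300 is 1.96·√(p(1 − p)/300): 2.7 points at p = 5.9% and 3.5 points at p = 11%. In the first model the shift at f = 10% is 0.9-1.9 points (p = 5.9%) or 0.4-1.4 points (p = 11%), inside that width. At f = 30% and q = 25% it is 5.7 and 4.2 points, outside it.

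**Association, outcome 6.** Assume a true 12% versus 6% (risk ratio 2.0), with the same f and q in both groups. For f = 10%, q = 15%: (0.9 × 12 + 1.5)/(0.9 × 6 + 1.5) = 12.3/6.9 = 1.78.

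| f | q = 15% | q = 25% |
|---|---|---|
| 10% | 1.78 | 1.68 |
| 20% | 1.62 | 1.49 |
| 30% | 1.48 | 1.36 |

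**The case against.** The strongest objection is that the gap is not proven. The outcome lists need not contain every question sent, and a question on new pregnancy is a covariate rather than an outcome. The count of 23 does not settle it, because the 12-month form also carries the recall question on acute pain and the request for renewed consent. The wording in Appendix 8 might even tie pain to the index cesarean. A part of the protocol between Inclusion Period and Patient characteristics was also missing from the copy read. This stands as a reason to look at Appendix 8 first. It does not change what the protocol text provides.

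Second, the size rests on assumed values. f and q come from nowhere in the protocol, p is borrowed from other definitions, and one q for vaginal births, cesareans and operations long past overstates the effect. The factor of 1.97 is the most extreme corner. At f = 10% the shift is within sampling error. All of this stands, so the figures are illustrations, not estimates.

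Third, the reach is narrow: the primary outcome is at 6 months, and the late prevalence and association outcomes are exploratory. This also stands, and it limits the weight of the point.

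Fourth, rules for such events could be left to the analysis plan, and dates might be recovered from records. The reporting rule could indeed sit there, but only if the events are captured, and record retrieval after day 30 is not now part of the plan.

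**Conclusion.** The concern holds. As written, the protocol can count pain after a repeat cesarean or other abdominal operation as persistent pain from the index cesarean, and nothing it lists would let an analyst tell them apart. The effect falls on assessments after 12 months, mainly at 2-5 years; the 6-month primary outcome and everything before it are essentially untouched.

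The direction is upward for prevalence when q exceeds p, and probably toward no association for uterine repair if later events are alike in both groups. The size cannot be derived from the protocol and ranges from negligible to larger than sampling error, depending on f and q. The conclusion is conditional on Appendix 8 holding no such question. It should be corrected because the remedy is cheap, but it does not threaten the main result.

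**What to change.** 1. Check Appendix 8 for a question on new pregnancy, delivery or surgery, and for wording that ties pain to the index cesarean.
2. If there is none, add one item from the 12-month questionnaire on: since the cesarean in this study, has the woman become pregnant, given birth (vaginally or by cesarean) or had abdominal surgery, and on what date. Alternatively, have the hospital data managers named under Data collection retrieve these dates from the health records. This also covers time points already passed.
3. In Data Processing and statistics, state that estimates at 12 months and later will be reported twice: for all assessments, and for assessments before the first new delivery or abdominal operation.

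The cost is one SMS item and a REDCap change, or a record search at each hospital, with a check that consent and the data approval cover it. The restricted estimate uses fewer assessments and may select women without a further pregnancy. If women in pain delay pregnancy, it will be too high. That is the reason to show both.

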### *Primary outcome*

The percentage of patients reporting pain equivalent to an NRS score > 3 after 6 months

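### The primary outcome can count pain that was already in the surgical area before the index cesarean, because it sets no condition on onset or worsening

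*Protocol*

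**What the plan says.** The Objective section states that the study aims to "describe the occurrence of persistent postoperative pain in a cohort of Danish patients who have undergone elective CD". Exploratory outcome 5 speaks of the development of persistent pain.

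The Outcomes section says that all pain outcomes "refer to pain in or around the surgical area". The primary outcome is "The percentage of patients reporting pain equivalent to an NRS score > 3 after 6 months". Together they fix site, intensity and time, but not onset or change from before the operation.

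Under Data collection, "The questionnaires are sent at fixed time intervals: at 5 weeks, 2 months, 3 months, 6 months, and 12 months", with later rounds at longer intervals. Under Informed consent, women are asked to join in the parent study's 30-day questionnaire. This study's own questionnaires are therefore all postoperative.

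The Inclusion criteria set no limit on earlier surgery or earlier pain. Patient characteristics records "Previous number of CD: 0, 1, 2, 3, or" four or more, previous laparoscopy or laparotomy, and, among the indications, a previous cesarean with no other reason. The only prior-pain item listed there is "Chronic pain patient, and/or receiving regular opioid and/or other pain treatment besides NSAIDs and PCM prior to pregnancy: Yes/No".

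The section on data processing and statistics plans three subgroup analyses: severe acute pain, uterine exteriorization, and chronic pain before pregnancy. None separates first from repeat cesarean.

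**The concern.** A woman with a scar from an earlier cesarean may have pain in that area before the index operation. If she rated it 4 before and rates it 4 six months after, she is a case for the primary outcome although nothing changed. Relative to new or worsened pain, this can only add cases, and a larger sample does not reduce it.

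The prior-pain item cannot sort these women out. It is one composite Yes/No without site or intensity, and its treatment limb leaves out NSAIDs and paracetamol. A woman with scar pain who is untreated, or takes only those drugs, is picked up only if she is recorded as a chronic pain patient.

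The associations are exposed too. Earlier local pain could plausibly raise both acute and late pain ratings, which bears on exploratory outcome 3. In exploratory outcome 5, if the pre-pregnancy chronic pain was in the scar area, predictor and outcome can be the same pain.

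**Working it through.** The protocol gives no figure for this point to reproduce. The sample is a convenience sample: half of 700 is 0.5 × 700 = 350, in line with the aim of at least 300.

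**Inputs**
- s, share with a previous cesarean: not given; assumed 30-60%.
- q, share of these with scar-area pain before the index cesarean: not given. As a stand-in, the Background figure from an earlier Danish single-center study, where "5.9% of the patients experienced pain from the cesarean scar area, daily or almost daily" (mean follow-up 10.2 months).
- f, share of those scoring above 3 at 6 months: not given; assumed 0.5-1.0.
- n = 350.

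**Carry-over = s × q × f**

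| s | q | f | Carry-over | Of 350 |
|---|---|---|---|---|
| 0.30 | 0.059 | 0.5 | 0.9 points | 3.1 |
| 0.30 | 0.059 | 1.0 | 1.8 points | 6.2 |
| 0.60 | 0.059 | 0.5 | 1.8 points | 6.2 |
| 0.60 | 0.059 | 1.0 | 3.5 points | 12.4 |

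**Sampling error for comparison: 95% half-width = 1.96 × √(p(1 − p)/n)**
- p = 5.9%: 1.96 × √(0.059 × 0.941/350) = 2.5 points
- p = 11%: 1.96 × √(0.11 × 0.89/350) = 3.3 points

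With n = 300 the half-widths are 2.7 and 3.5 points. At the upper end of the assumptions the carry-over is thus about as large as the sampling error; at the lower end it is well below it.

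**Dependence on q.** The Background also cites a review range of 11-27% for pain after six months. Putting its lower end in place of 5.9% gives 0.30 × 0.11 × 0.5 = 1.65 points to 0.60 × 0.11 × 1.0 = 6.6 points. That is not a better estimate, since neither source figure is a prevalence of NRS above 3. It shows how far the result depends on an unknown.

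The carry-over is a gross count: some of these women may have pain that became worse after the index cesarean and would rightly count.

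**The case against.** The strongest reply is that the primary outcome is correct as worded: it is a prevalence of surgical-area pain at 6 months and claims neither incidence nor cause. That stands in part. A reader might infer that the objective is pain caused by this operation, but the Objective section does not say so. The mismatch rests on the word postoperative there and on development in exploratory outcome 5. It concerns what the percentage can be taken to mean.

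The prior-pain item should not be read too narrowly either. Its first limb needs no treatment, so a woman with untreated chronic scar pain can be coded Yes. It could miss such women; the text does not show that it must.

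A reader might also infer that no localised baseline exists anywhere. The documents do not support that. The parent study's forms and the question list in Appendix 8 are not shown and could hold one. This protocol neither lists nor uses one.

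Finally, the choice of strata is often left to a statistical analysis plan, which may exist. That is fair for a restricted analysis by itself, but no analysis plan can supply a baseline that was not measured.

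**Conclusion.** The point holds as a limit on interpretation. As written, the primary percentage can include pain carried over from before the index cesarean, so it can overstate the persistent postoperative pain that the study aims to describe. Exploratory outcome 5 can be partly circular.

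The size is unknown. The illustration of 0.9-3.5 percentage points, or 3-12 of 350 women, rests on three inputs that the protocol does not give: the share with a previous cesarean, the share of these with prior local pain, and how many of them score above 3 at 6 months.

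It is tempting to turn this into a share of cases. Setting 1.8-3.5% against an observed 6-10% would give 1.8/10 = 18% to 3.5/6 = 59%. The documents do not support that range. It lets every woman with old scar pain score above 3, and its denominator is assumed and lies below the cited 11-27%. Against that range the same numerators give 1.8/27 = 7% to 3.5/11 = 32%, and half as much if only half score above 3. The 11-27% is itself any pain, so none of these shares should be relied on.

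**What to change.** 1. **Restricted analysis.** Beside the whole cohort, report the primary outcome and exploratory outcomes 3 and 6 in women with no previous cesarean, no previous abdominal surgery and no chronic pain before pregnancy. For exploratory outcome 5, chronic pain is the exposure, so restrict by earlier surgery only. All variables are already collected. The cost is a smaller subset and a wider interval.

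2. **Baseline.** Use any localised preoperative pain data held in the parent study. If there are none, add one question on whether there was pain in this area before this cesarean and, if so, whether it was less than, the same as or more than now. Label it as recalled, and use it only for a sensitivity analysis of new or worse pain, not to reclassify primary cases. It adds one item to a 23-question form that takes under 5 minutes, and exploratory outcome 1 already relies on recall. The cost is recall error, which may be coloured by current pain and may be considerable, since inclusion was scheduled to end on 30.07.2024.

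3. **Wording.** Describe the whole-cohort primary result as the prevalence of pain in the surgical area at 6 months, not as pain newly arising from the index cesarean. This costs nothing and is the minimum.
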